4.4 Interim Analysis and Data Base Lock

An unblinded analysis will be conducted after all subjects have completed Week 24 for the purpose of regulatory submission. Study sites and subjects will remain blinded for the duration of Period 1. Additional unblinded analysis may be conducted after the Week 24 unblinded analysis.

4.5 Data Monitoring Committee (DMC) Activities

An independent external Data Monitoring Committee (DMC) is used to review unblinded safety data at regular intervals during the conduct of the study. The DMC will provide recommendation to an AbbVie Point of Contact on whether to continue, modify, or terminate studies after each review. When needed, high-level unblinded efficacy data may also be requested by the DMC and be reviewed so that the DMC can assess benefit: risk of any emerging safety differences.

5.0 Analysis Populations and Analysis Windows

5.1 Analysis Populations

Full Analysis Set (FAS)

The Full Analysis Set (FAS) includes all randomized subjects who received at least one dose of study drug. The FAS will be used for all efficacy and baseline analyses.

Per Protocol Analysis Set

The Per Protocol Analysis Set represents a subset of the FAS and consists of all FAS subjects who did not meet any major protocol deviations prior to Week 24 of the study. Additional analysis of the primary efficacy endpoint will be conducted on the Per Protocol analysis set, in order to evaluate the impact of major protocol deviations.

Major protocol deviations (ICH deviations and other clinically significant non-ICH deviations) will be identified prior to database lock.

Safety Analysis Set

The Safety Analysis Set consists of all subjects who received at least one dose of study drug. For the Safety Analysis Set, subjects are assigned to a treatment group based on the "as treated" treatment group, regardless of the treatment randomized. The "as treated" is determined by the treatment the subject received during the majority of the subject's drug exposure time in the analysis period.

For all analysis sets, global analyses are performed on the treatment groups of MTX, Upadacitinib 15 mg QD, Upadacitinib 30 mg QD, including all subjects enrolled under these three treatment groups. Japan sub-study analyses are performed on the treatment groups of MTX, Upadacitinib 7.5 mg QD, Upadacitinib 15 mg QD, Upadacitinib 30 mg QD, including only subjects enrolled in Japan.

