### **8.1.1.2 Per Protocol Analysis Set**

The Per Protocol Analysis Set represents a subset of the FAS and consists of all FAS subjects who did not meet any major protocol violations during the study. Definitions of major protocol violations will be detailed in the SAP. Additional analysis may be conducted on the Per Protocol analysis set, in order to evaluate the impact of major protocol violations.

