6.4 Protocol Deviations

Protocol deviations are categorized as follows:

- Those who entered the study even though they did not satisfy the entry criteria
- Those who developed withdrawal criteria during the study and were not withdrawn
- Those who received the wrong treatment or incorrect dose, and
- Those who received an excluded or prohibited concomitant medication.

The protocol deviations listed above and other significant protocol deviations will be summarized and listed by treatment group.

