9.2 Efficacy Analysis for the Primary and Key Secondary Endpoints

9.2.1 Primary Efficacy Analysis

The primary endpoint for US/FDA regulatory purposes is the proportion of subjects achieving ACR50 response at Week 12. The primary endpoint for EU/EMA regulatory purposes is the proportion of subjects achieving Clinical Remission (CR) (defined by DAS28(CRP) < 2.6) at Week 24. For Japan/PMDA regulatory purposes, the primary endpoints are the proportion of subjects achieving ACR20 response at Week 12 and change from baseline in modified Total Sharp Score (mTSS) at Week 24. Analyses will be conducted separately for US/FDA, EU/EMA and Japan/PMDA regulatory purposes.

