9.2.2 Sensitivity Analysis of Primary Efficacy Variables

The analysis of ACR20 and ACR50 at Week 12 will be repeated using Observed Cases and the analysis of CR at Week 24 will be repeated using As Observed as a sensitivity analysis without any imputation. These analyses will be conducted on the FAS based on randomized treatment groups.

Supportive NRI analysis for ACR20, ACR50 and CR and supportive linear extrapolation and AO analysis for change from baseline in mTSS will also be conducted on the Per Protocol Analysis Set.

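### The single Per Protocol set is cut at Week 24 but is also used for ACR50 and ACR20 at Week 12, so a deviation after the Week 12 assessment can exclude a subject from a Week 12 analysis and may bias it

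*SAP*

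**What the plan says.** SAP 5.1 defines the Per Protocol set as one that "consists of all FAS subjects who did not meet any major protocol deviations prior to Week 24 of the study". It gives one cut-off for all endpoints and adds that "Additional analysis of the primary efficacy endpoint will be conducted on the Per Protocol analysis set", to evaluate the impact of major deviations. Protocol 8.1.1.2 is wider still: its set takes FAS subjects who "did not meet any major protocol violations during the study".

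Two of the primary endpoints are at Week 12. SAP 9.2.1 states: "The primary endpoint for US/FDA regulatory purposes is the proportion of subjects achieving ACR50 response at Week 12". For Japan/PMDA purposes "the primary endpoints are the proportion of subjects achieving ACR20 response at Week 12", together with mTSS at Week 24. SAP 9.2.2 plans, on the Per Protocol set, "Supportive NRI analysis for ACR20, ACR50 and CR and supportive linear extrapolation and AO analysis" for mTSS. SAP Table 6, which covers Week 12, lists the same set as supportive for both ACR50 and ACR20. Neither document defines a Week 12 version.

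SAP 5.1 describes major deviations as ICH deviations and other clinically significant non-ICH deviations, to be identified before database lock. SAP 6.4 lists the categories to be summarised. Several can arise after Week 12: wrong treatment or dose, not being withdrawn when withdrawal criteria are met, and "Those who received an excluded or prohibited concomitant medication".

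**The concern.** A Per Protocol analysis of a Week 12 endpoint should show whether deviations that could have influenced that endpoint matter. Applying the Week 24 cut-off to it makes inclusion depend on what happens afterwards. If those later events are related to the Week 12 result, the retained subjects are a selected group, and the selection can differ between arms.

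The protocol contains routes by which this could happen:

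- Background medication may not be started outside the rescue rules (Protocol 5.2.3.1). Joint-count rescue needs failure at two consecutive visits from Week 12 (Protocol 5.2.3.3), so it first becomes available at Week 16. A subject doing poorly at Week 12 who is given such medication before qualifying has deviated.
- A subject with at least 20% joint-count improvement but no ACR50 response does not qualify for rescue before Week 26. Medication started for that subject earlier is also a deviation.
- Investigator-judged non-response is one of the grounds for stopping study drug in Protocol 5.4.1. A subject who meets it and is not withdrawn falls into a SAP 6.4 category.

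At stake is whether the supportive Week 12 analyses for the US and Japan can be read as a check on the impact of deviations.

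**Working it through.** **Planning inputs** (Protocol 8.2, SAP 4.3): 900 subjects in three arms, taken as 300 per arm; 10% dropout, so 300 × 0.9 = 270; two-sided α = 0.025; ACR50 at Week 12 20% on MTX and 40% on upadacitinib; ACR20 at Week 12 50% and 70%.

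**The plan's own figures.** At 270 per arm the power is 99.8% for ACR50, 99.5% for ACR20 and 96.2% for CR (each stated as at least 90%), and 79.4% for mTSS (stated as approximately 80%). The planning figures reproduce; they serve here only as inputs.

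**Selection effect.** Let p be the true Week 12 response rate in an arm. Let dR and dN be the shares of its Week 12 responders and non-responders removed for a deviation between Weeks 12 and 24. The rate among those retained is

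p_PP = p(1 − dR) / [p(1 − dR) + (1 − p)(1 − dN)].

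The documents give no values for dR or dN, so every value below is an assumption.

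*Removal unrelated to response* (dR = dN = 5%): ACR50 stays at 20.0% and 40.0%, and ACR20 at 50.0% and 70.0%. There is no bias.

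*Same selection in both arms:*

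| dR | dN | ACR50 MTX / upadacitinib | Difference | ACR20 MTX / upadacitinib | Difference |
|---|---|---|---|---|---|
| 2% | 5% | 20.5 / 40.7 | 20.2 | 50.8 / 70.7 | 19.9 |
| 2% | 10% | 21.4 / 42.1 | 20.7 | 52.1 / 71.8 | 19.6 |
| 0% | 20% | 23.8 / 45.5 | 21.6 | 55.6 / 74.5 | 18.9 |

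The same selection widens the ACR50 difference and narrows the ACR20 difference.

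*Selection that differs by arm* (ACR50, dR = 2% in both):

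- dN 15% on MTX, 5% on upadacitinib: 0.196/(0.196 + 0.680) = 22.4% and 0.392/(0.392 + 0.570) = 40.7%. The difference is 18.4 points instead of 20.0.
- dN 5% on MTX, 15% on upadacitinib: 0.196/(0.196 + 0.760) = 20.5% and 0.392/(0.392 + 0.510) = 43.5%. The difference is 23.0 points.
- dN 20% on MTX, 5% on upadacitinib: 0.196/(0.196 + 0.640) = 23.4% and 40.7%. The difference is 17.3 points.
- True rates of 20% in both arms, dN 15% against 5%: 22.4% and 20.5%, a spurious difference of 1.9 points against the arm that loses fewer non-responders.

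**With a Week 12 cut-off**, events after the assessment remove nobody from the Week 12 analysis, and the planned rates are not altered by them.

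**The case against.** The strongest reply is that the link between later deviations and Week 12 response is not shown. Rescue that follows the protocol is permitted, including corticosteroids within its limits between Weeks 12 and 24 (Protocol 5.2.3.2 and 5.2.3.3), and neither document calls it a deviation. For the poorest responders, much of the added medication would therefore be allowed. Most stopping criteria in Protocol 5.4.1 concern safety or compliance; the one response-related item that applies before Week 48 is left to the investigator, and the joint-count stopping rule starts at Week 48. Missed safety withdrawals could as easily fall on upadacitinib. SAP 6.4 lists categories for summary and does not say that they are the exclusion list, so how many post-Week 12 events would exclude a subject is unknown. All of this stands.

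Two stronger readings are therefore tempting but unsupported. A reader might infer that the set removes non-responders selectively and more often on MTX; the documents show only that this can happen, and the direction is open. A reader might also infer that any disagreement between FAS and Per Protocol results would be an artefact. Entry-criteria violations and dosing errors before Week 12 also separate the two sets, and measuring their impact is the purpose of the set.

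It is also true that the analysis is supportive and that Week 12 has a second check, Observed Cases on the FAS (SAP 9.2.2), which does not exclude subjects for later protocol deviations. This limits the weight of the point but does not justify the cut-off. The regulatory analyses are separate, so nothing requires one common cut-off, and the SAP already treats the two time points differently by using Observed Cases at Week 12 and As Observed at Week 24.

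**Conclusion.** The point holds in a limited form. By its stated rule, the plan removes subjects from the supportive Week 12 ACR50 and ACR20 analyses for events that cannot affect those outcomes. Where such events depend on Week 12 response, the estimate can be biased upward or downward, and part of any FAS versus Per Protocol difference could reflect the definition of the set. Agreement between the two is likewise harder to read as evidence of robustness.

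The size rests wholly on assumed removal rates: about 0 to 3 points on an ACR50 difference of 20 (17.3 to 23.0 in the scenarios shown), about 0 to 1 point for ACR20 under common selection, and none if removal is unrelated to response. With planned differences this large, shifts of that order would be unlikely to reverse the supportive conclusion. The FAS non-responder analysis, the multiplicity procedure and the Week 24 Per Protocol analyses of CR and mTSS, where the cut-off fits the endpoint, are not affected. The change is worth making but is not critical.

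**What to change.** Define the Per Protocol set by endpoint in SAP 5.1: no major deviation up to the subject's Week 12 assessment for ACR50 and ACR20, and none up to the Week 24 assessment for CR and mTSS. For a subject without a Week 12 assessment, the target day in SAP Table 1 (Day 85) could serve as the cut-off. SAP 9.2.2 and Table 6 should then refer to the Week 12 version.

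SAP 11.1 says that the primary analysis and Period 1 reporting were completed under version 2.0 and that the current update applies only to future long-term reporting. Editing 5.1 alone would therefore change no Week 12 result. The Week 12 version should be run as a labelled post hoc sensitivity analysis, with the number of subjects in each arm excluded only for deviations after Week 12, split by Week 12 response. That count would replace the assumed rates above.

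The cost is one extra population flag from dated deviations and one re-run of a supportive table. If no re-run is made, a caveat beside the reported Week 12 Per Protocol results is the minimum.

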5.2 Analysis Windows

Definition of Study Days (Days Relative to the First Dose of Study Drug)

Study Days are calculated for each collection date relative to the date of the first dose of study drug. It is defined as the number of days between the date of the first dose of study drug and the collection date. Study days are negative values when the collection date of interest is prior to the first study drug dose date. Study days are positive values when the collection date of interest is on or after the first study drug dose date. The day of the first dose of study drug is defined as Study Day 1, while the day prior to the first study drug dose is defined as Study Day –1 (there is no Study Day 0). Study days are used to map actual study visits to the protocol-specified study visits.

Definition of Analysis Windows

The following rules will be applied to assign actual subject visits to protocol-specified visits. For each protocol-specified study visit, a target study day will be identified to represent the corresponding visit along with a window around the target day. Windows will be selected in a non-overlapping fashion so that a collection date does not fall into multiple visit windows. If a subject has two or more actual visits in one visit window, the visit closest to the target day will be used for analysis. If two visits are equidistant from the target day, then the later visit will be used for analysis.

The visit window and the target study day for each protocol-specified visit in Period 1 are displayed in [Table 1](#), [Table 2](#) and [Table 3](#) (depending on the different visit schedules of different endpoints). Visit windows for protocol-specified visits in Period 2 are defined similarly.

Table 1. Analysis Windows for Efficacy Analysis for Period 1 (for ACR Components and Morning Stiffness) and Safety Analysis for Period 1 (for Labs and Vital Signs)

Protocol Specified Visit Week	Lower Bound	Target Day	Upper Bound
Baseline	-99	1 ^a	1
2	2	15	22
4	23	29	43
8	44	57	71
12	72	85	99
16	100	113	127
20	128	141	155
24	156	169	176
26	177	183	190
28	191	197	211
32	212	225	239
36	240	253	267
40	268	281	309
48	310	337	379

a. Day of first dose of study drug.

Table 2. Analysis Windows for Efficacy Analysis for Period 1 (for EQ-5D-5L, FACIT-F, WPAI and SF-36)

Protocol Specified Visit Week	Lower Bound	Target Day	Upper Bound
Baseline	-99	1 ^a	1
12	2	85	127
24	128	169	253
48	254	337	421

a. Day of first dose of study drug.

Table 3. Analysis Windows for Efficacy Analysis for Period 1 (for mTSS Endpoints)

Protocol Specified Visit Week	Lower Bound	Target Day	Upper Bound
Baseline	-99	1 ^a	1
12*	2	85	127
24	128	169	197
36*	198	253	295
48	296	337	379

a. Day of first dose of study drug.

* Week 12 and 36 are not protocol specified visits for Xray assessments, but will be used to capture unscheduled or PD x-rays.

Table 4. Analysis Windows for Efficacy Analysis for Period 1 (for IgG and IgM)

Protocol Specified Visit Week	Lower Bound	Target Day	Upper Bound
Baseline	-99	1 ^a	1
8	2	57	113
24	114	169	253
48	254	337	421

a. Day of first dose of study drug.

6.0 Demographics, Baseline Characteristics, Medical History, and Previous/Concomitant Medications

6.1 Demographics and Baseline Characteristics

Demographic and baseline characteristics information will be collected at the Baseline visit of the study and will be summarized for the FAS. The number of observations, mean, standard deviation, median, minimum and maximum will be summarized for continuous variables. Categorical or discrete variables will be summarized via frequencies and percentages. Summary statistics will be computed for each treatment group and overall.

Main Demographic and Baseline Characteristics

- Sex (male/female)
- Age (years)
- Age Categories (< 40, [40, 65), ≥ 65 years)
- Race (White, Black or African American, American Indian or Alaska Native, Native Hawaiian or Other Pacific Islander, Asian, Other)
- Geographic Region (North America, South/Central America, Western Europe, Eastern Europe, Asia-Japan, Asia-Other, Other)
- Ethnicity (Hispanic or Latino, Not Hispanic or Latino)
- Weight (kg)
- Weight Categories (< 60 kg, ≥ 60 kg)
- Height (cm)
- Body Mass Index (BMI) (kg/m²)
- Body Mass Index (BMI) Category (kg/m²) (BMI < 25 vs BMI ≥ 25)

RA Medical History and Characteristics

- Duration of RA Symptoms
- Duration of RA Diagnosis
- Duration of RA Symptoms Categories (< 2 years or ≥ 2 years)
- Duration of RA Diagnosis Categories (< 6 months or ≥ 6 months)

ACR and/or DAS Components at Baseline

- Tender joint count (TJC68) defined as the number of tender joints out of 68 assessed joints
- Swollen joint count (SJC66) defined as the number of swollen joints out of 66 assessed joints
- Tender joint count (TJC28) defined as the number of tender joints out of 28 assessed joints used for DAS28 calculation

- Swollen joint count (SJC28) defined as the number of swollen joints out of 28 assessed joints used for DAS28 calculation
- Physician's global assessment of disease activity (mm on a 100-mm horizontal visual analogue scale [VAS])
- Patient's assessment of pain within last week (mm on a 100-mm horizontal [VAS])
- Patient's global assessment of disease activity within last 24 hours (mm on a 100-mm horizontal VAS)
- Health Assessment Questionnaire Disability Index of the (HAQ - DI) (range: 0 to 3)
- High sensitivity C-reactive protein (hsCRP) (mg/L)
- Erythrocyte sedimentation rate (ESR) (mm/hr)

Other Baseline RA Disease Characteristics

- Anti-cyclic citrullinated peptide (Anti-CCP) (units)
- Anti-CCP status: Positive or Negative
- Rheumatoid Factor (RF) (units)
- Rheumatoid Factor (RF) status: Positive or Negative
- RF and Anti-CCP both positive vs. at least one negative
- RF and Anti-CCP both negative vs. at least one positive
- DAS28 [hsCRP]
- DAS28 [ESR]
- DAS28 Categories:
 - DAS28 > 5.1 (High Disease Activity)
 - DAS28 ≤ 5.1
- Clinical Disease Activity Index (CDAI)
- CDAI categories:
 - CDAI > 22 (High Disease Activity)
 - CDAI ≤ 22
- Simplified Disease Activity Index (SDAI)

- SDAI categories:
 - SDAI > 26 (High Disease Activity)
 - SDAI ≤ 26
- Modified Total Sharp Score (mTSS)
 - Modified Total Sharp Score (mTSS)
 - Erosion score
 - Joint space narrowing score

Patient Reported Outcomes at Baseline

- Morning stiffness (severity and duration)
- Functional Assessment of Chronic Illness Therapy-Fatigue (FACIT-F)
- Work Productivity and Activity Impairment Questionnaire (WPAI)
- 36-Item Short Form Health Survey (SF-36) Version 2: physical component summary, mental component summary and the 8 sub-domain scores
- EQ-5D-5L

Clinical Tests at Screening

- Chest x-ray
- ECG
- Tuberculin PPD skin test, QuantiFERON TB Gold test
- Serum pregnancy test

Immunization History

- BCG immunization
- Herpes Zoster immunization
- Hepatitis B immunization

Tobacco/Nicotine and Alcohol Use

- Tobacco/Nicotine Use [user, ex-user, non-user, unknown]
- Alcohol Use [drinker, ex-drinker, non-drinker, unknown]

6.2 Medical History

Medical history data will be summarized and presented for FAS population using body systems and conditions/diagnoses as captured on the CRF. The body systems will be presented in alphabetical order and the conditions/diagnoses will be presented in alphabetical order within each body system. The number and percentage of subjects with a particular condition/diagnosis will be summarized for each randomized treatment group as well as overall. Subjects reporting more than one condition/diagnosis within a body system will be counted only once for that body system. No statistical comparison will be performed for medical history reporting.

6.3 Prior Treatment and Concomitant Medications

Prior and concomitant medications will be summarized by each randomized treatment group as well as overall for FAS. Prior medications are those medications taken prior to the first dose of study drug. This includes medications with a start date before the first study drug administration date, regardless of the end date of these medications. Medications taken on the day of the first dose of study drug are not counted as prior medications. Concomitant medications are those medications, other than study drug, taken after the first dose of study drug and within 7 day of the last dose of study drug. This includes medications with a start date between first study drug administration and last study drug administration + 7 day, as well as, medications with a start date prior to first dose of study drug and which are ongoing after first dose of study drug. Medications taken on the day of the first dose of study drug are counted as concomitant medications.

The number and percentage of subjects who received a prior medication and the number and percentage of subjects who received a or concomitant medication will be tabulated

separately by the generic name assigned by the most current version of the World Health Organization (WHO) Drug Dictionary.

6.4 Protocol Deviations

Protocol deviations are categorized as follows:

- Those who entered the study even though they did not satisfy the entry criteria
- Those who developed withdrawal criteria during the study and were not withdrawn
- Those who received the wrong treatment or incorrect dose, and
- Those who received an excluded or prohibited concomitant medication.

The protocol deviations listed above and other significant protocol deviations will be summarized and listed by treatment group.

7.0 Patient Disposition

The following will be summarized by randomized treatment group as well as overall:

- number of subjects randomized,
- number of subjects included in key analysis populations (Full Analysis Set and Per Protocol Analysis Set for primary efficacy analysis, Safety Analysis Set),
- number of subjects on-going in Period 1 (if applicable)
- number of subjects who completed Period 1 study participation,
- number of subjects who entered Period 2,
- number of subjects who completed overall study (Period 1 and Period 2) participation (if applicable).

This summary will be repeated by site.

Premature discontinuation details will be further summarized separately for Period 1 and Period 2 as follows.

Period 1

The number and percentage of subjects completed Period 1 and prematurely discontinued in Period 1 will be summarized separately by study drug and study participation completion/discontinuation, with the reasons for discontinuation collected from CRF by the following categories:

- Adverse event (AE)
- Withdrew consent
- Lost to follow-up
- Lack of efficacy
- Other.

Study participation completion/discontinuation will be summarized for Period 1 by randomized treatment group and by treatment sequence, respectively.

Study drug completion/discontinuation will be summarized as follows:

- By randomized treatment group: number and percentage of completion by Week 26 and by Period 1, number/percentage and primary reason for discontinuation by Week 26 and between Week 26 to end of Period 1;
- By treatment sequence: number/percentage and primary reason for discontinuation between Week 26 to end of Period 1. Refer to Section 9.1 for the definition of treatment sequences.

Subjects may have more than one reason for discontinuing, but only the primary reason will be summarized.

In addition, the number and percentage of subjects enrolled in Period 2 will also be summarized.

For Week 24 reporting, study drug completion/discontinuation will only be summarized by randomized treatment group based on the number and percentage of completion by

Week 24 and based on the number/percentage and primary reason for discontinuation by Week 24.

Period 2

Period 2 patient dispositions and reason for discontinuation will be summarized for overall, by treatment group sequences (as defined in Section 9.1), and by treatment regimens when entering Period 2 defined as follows:

